Although anabolic steroids may increase muscle mass and strength, lack of oral bioavailability and known potential risks have limited their use. Selective androgen receptor modulators (SARMS) have great potential to achieve similar benefits of anabolic steroid therapy (improved muscle mass, cholesterol/triglyceride levels, glucose metabolism, and bone density) with fewer adverse effects, such as hirsutism and acne, in women.

SARMS may provide a new therapeutic option for pelvic floor and lower urinary tract disorders, as both testosterone and its more potent metabolite converted by 5- α reductase, dihydrotestosterone (DHT), have anabolic effects on muscle. The potential for SARMS as a treatment for SUI is strengthened by studies showing that urethral closure pressure is the factor most strongly associated with SUI (Delancey, 2007; Delancy, 2008). This finding is supported by both morphological and electromyographic (EMG) evidence. In imaging studies, the striated urethral sphincter has been found to be smaller in women with SUI compared to continent controls (Athanasίου, 1999; Morgan; 2009). In EMG studies, the striated urethral sphincters of women with SUI exhibit smaller EMG amplitudes and shorter motor-unit-potential durations, with more phases, than continent controls (Kenton, 2011; Takahashi, 2000), indicating primarily

myogenic changes. Furthermore, it is well accepted that pelvic floor muscle (PFM) rehabilitation is an effective treatment for SUI (Hay-Smith, 2009). PFM rehabilitation may be effective because it strengthens not only the pelvic floor but may also strengthen the striated urethral sphincter. This idea is supported by a recent publication that reported, based on ultrasound (US), a 12-week PFM exercise program produced a significant increase in the cross-sectional area of the urethra, at the level of the striated urethral sphincter, in middle-aged women (McLean, 2013). Because of limits in the resolution of US images, the authors were not able to determine which part of the urethra hypertrophied. The investigators suggested that PFM rehabilitation in older women with SUI could condition the striated urethral sphincter leading to measurable hypertrophy, observable on MRI.

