4. METHODOLOGY

4.1 STUDY DESIGN

This is a single site, proof of concept feasibility study to describe the effect of GTx-024 3 mg in postmenopausal female subjects with SUI. Postmenopausal will be defined as clinically confirmed female subjects who have undergone the onset of spontaneous, medical or surgical menopause prior to the start of this study. Durability of treatment will also be explored by evaluating validated measures at 4 weeks after last dose. Up to 35 subjects will be enrolled in this study.

Institutional Review Board (IRB) approval from Beaumont's Human Investigations Committee will be obtained prior to beginning any study activity. Once IRB approval is obtained, potential participants will be identified from existing medical records, or physician or other referrals.

Potential subjects may be prescreened by telephone prior to the first in person study visit (initial screening visit). At the first in person study visit, subjects will be seen in the Urology Clinical Research space and informed consent will be obtained prior to any study activity. At Study Visit, 2, inclusion/exclusion criteria will be verified, study data will be collected, and consented participants may begin treatment.

Enrolled subjects will agree to maintain on a stable dose of any medication known to affect lower urinary tract function, including but not limited to anticholinergics, tricyclic antidepressants, or alpha-adrenergic blockers, throughout the treatment and follow-up period. Subjects enrolled in the study will agree to not start any new treatment (medication or otherwise) that is known to affect lower urinary tract function throughout the treatment and follow up periods. Subjects will also agree to refrain from performing any Kegal exercises and maintain current dietary habits throughout the treatment and follow up periods.

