5. STUDY ENROLLMENT AND WITHDRAWAL

5.1 SUBJECT INCLUSION CRITERIA

Subject Inclusion Criteria: Subjects eligible for inclusion in this study must meet **all** of the following criteria:

1. Give voluntary, written and signed, informed consent
2. Female
3. Age 18 to 80 years old
4. Clinically confirmed as postmenopausal. Subjects must have undergone the onset of spontaneous, medically induced or surgical menopause prior to the start of this study. Postmenopausal is defined as 12 months of spontaneous amenorrhea or 6 months of spontaneous amenorrhea with serum FSH levels > 40 mIU/ml or 6 weeks postsurgical bilateral oophorectomy with or without hysterectomy.
5. SUI symptoms for at least 6 months duration
6. Predominant SUI (MESA questionnaire)
7. 24 hour pad weight >3 gms at baseline
8. At least 4, but no more than 15, SUI episodes on each day of the 3 day baseline voiding diary.
9. Serum AST and ALT within normal limits
10. Total bilirubin within normal limits
11. Positive Bladder Stress Test
12. Subject agrees to not start any new treatment (medication or otherwise) that is known to affect lower urinary tract function throughout the treatment and follow up periods.
13. Subject agrees to maintain on a stable dose of any medication known to affect lower urinary tract function, including but not limited to anticholinergics, tricyclic antidepressants, or alpha-adrenergic blockers, throughout the treatment and follow-up period.

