5.2 SUBJECT EXCLUSION CRITERIA

Subject Exclusion Criteria: Subjects eligible for this study must not meet any of the following criteria:

1. Pelvic floor physical therapy within the last 6 months
2. History of pelvic radiation treatment
3. History of urethral diverticula
4. History of urethral sling, anterior prolapse repair, ureteral bulking agents and/or other SUI procedure or surgery
5. Known vesicoureteral reflux, vaginal prolapse beyond the introitus, or other significant pelvic floor abnormalities
6. Patient has urinary incontinence of neurogenic etiology
7. Patient is morbidly obese (defined as 100 pounds over their ideal body weight, or body mass index 40 or greater)
8. Chronic hepatitis
9. Hepatic cirrhosis
10. HIV and/or hepatitis A, B, or C

11. Subjects taking systemic hormone products (excludes intravaginal application of estradiol topical/tablet agents and hormones delivered via vaginal rings)
12. Subjects with a history of breast or endometrial cancer.
13. Subjects with cerebrovascular disease, thromboembolic disorders, myocardial infarction, or angina.
14. Subject with an entry measurement of > 5 mm endometrial stripe thickness as measured by MRI.
15. Any other condition which per investigators' judgement may increase subject risk
16. Clinically confirmed urinary tract infection

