7. STUDY SCHEDULE

7.1 STUDY VISITS

Each subject may complete up to 5 months of study participation.

Screening Visit, Days -21-0

The study will be explained in detail and adequate time will be allowed for answering potential subjects questions prior to signing the IRB approved informed consent document. Informed consent will be obtained from those volunteers meeting initial inclusion/exclusion criteria and expressing willingness to participate prior to conducting any further study tests or measures.

Once informed consent is obtained, a detailed interview with vital signs will be conducted to further review for inclusion/exclusion criteria. A subject number will be assigned. Height and weight will be measured. Subjects will complete the MESA questionnaire to assess incontinence type (stress, urge, or mixed). If urinary incontinence type is stress predominant, then the subject will be instructed to complete a 24 hour pad weight and 3 day voiding diary prior to the next study visit. A bladder

stress test will be done to confirm SUI. Lab tests will also be drawn at this visit as outlined in Table I. A baseline urinalysis will be obtained. Concomitant medications will also be assessed and recorded.

Additional Screening, Days -21-0

If the subject has qualified for the study during the Screening visit, the following procedures will be performed between Screening Visit and Visit 1. Mammogram, if not done within the last 6 months, will be performed. Pelvic MRI will be performed

Study Visit 1: Week 0, Clinic Visit

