Subjects still meeting inclusion/exclusion criteria after all Screening study measures have been completed and reviewed will return for Visit 1 where the 24 hour pad weight and 3 day voiding diary will be collected and reviewed. An interview with vital signs will be conducted. A detailed medical history will be taken, including past gynecological and obstetric history (gravida, para, prior abortions and deliveries) and a focused physical exam, including standard gynecological pelvic exam and skin assessment, will be done. Urine dipstick will be done and PVR will be measured. If subject still meets inclusion/exclusion criteria, UPP will be performed. A dose of Ciprofloxacin or equivalent will be given prophylactically to prevent bladder infection. Serum lab tests consisting of a CBC, lipid panel and testosterone level will be drawn. Questionnaires (UDI-6, IIQ, FSFI, and PGI-S) will also be completed at this visit. Concomitant medications and adverse events, will be assessed and recorded. A baseline MRI measurement will be scheduled and/or completed prior to receiving study drug.

Subjects who meet all the inclusion and none of the exclusion criteria will receive study drug. Study drug will be packaged in bottles. Each study drug bottle will be preprinted with a Medication ID number. The Medication ID number assigned to the subject will be noted in the case report form (CRF) for study drug.

The first dose of study drug will be taken during this visit if the subject meets all criteria for enrollment. A one month supply of study drug (35 count bottles) will be dispensed with administration instructions.

Study Visit 2: Week 1, Phone Call

Approximately 1 week after beginning treatment, subjects will be contacted by phone to assess for concomitant meds and adverse events. Subjects will also be instructed to complete a 24 hour pad weight and 3 day voiding diary within the week preceding their next study visit.

Study Visit 3: Week 4, Clinic Visit

Approximately 4 weeks after beginning treatment, subjects will return to the clinical research office for an in person visit. An interview with vital signs will be conducted. Height and weight and PVR will be measured. Pad weights will be measured, and the 3 day voiding diary will be collected and reviewed. Blood will also be drawn to measure serum AST, ALT, and total bilirubin. Questionnaires will also be completed, and

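### The Kegel ban starts with treatment, after the baseline measures, so a woman who stops home exercise at first dose could carry that loss into her change from baseline

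*Combined protocol and SAP*

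**What the plan says.** Section 4.1 sets the exercise rule: "Subjects will also agree to refrain from performing any Kegal exercises and maintain current dietary habits throughout the treatment and follow up periods". It names two periods, and screening is not one of them.

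The only entry criterion that touches pelvic floor exercise is exclusion 1 in Section 5.2: "Pelvic floor physical therapy within the last 6 months". Kegel or home exercise is not named in Section 5.1, in Section 5.2, in the criteria repeated in the Protocol Summary, or among the forbidden treatments in Section 6.8. Inclusion 12 deals with starting something ("Subject agrees to not start any new treatment (medication or otherwise") and inclusion 13 with medicines ("Subject agrees to maintain on a stable dose of any medication known to affect lower urinary tract function"). Neither covers a woman who stops a non-drug habit she already has.

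Section 7.1 places the baseline measures before dosing. For a woman whose leakage proves at Screening to be mainly of the stress type, the instruction reads: "then the subject will be instructed to complete a 24 hour pad weight and 3 day voiding diary prior to the next study visit". For imaging, "A baseline MRI measurement will be scheduled and/or completed prior to receiving study drug". The urethral pressure profile is described at Visit 1, ahead of the first capsule.

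Section 2.1 states that "it is well accepted that pelvic floor muscle (PFM) rehabilitation is an effective treatment for SUI", and reports that "a 12-week PFM exercise program produced a significant increase in the cross-sectional area of the urethra".

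Sections 3.3 and 10.1 define the primary endpoint as change from Baseline to Week 12 in daily stress leaks, tested with an exact Wilcoxon signed rank test. There is no control arm.

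**The concern.** For a woman already exercising at home, two things may change on the day of the first dose: she starts the drug and she stops a therapy that the protocol regards as effective. Her Week 12 values would then reflect the drug plus 12 weeks without exercise. No comparison group loses the same benefit, so the two cannot be separated.

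Inclusion 12 already bars new treatments of any kind that affect the lower urinary tract. The added force of the Kegel ban therefore falls mainly on women who exercise at entry, who are the ones for whom it creates a change between baseline and Week 12.

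The likely direction is more leaks and lower closure pressure, which would understate benefit. That matters because Section 10.1 looks ahead to using the estimates for effect size and sample size in later trials.

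**Working it through.** The plan has no figure of its own on this point: it gives no share of exercisers, no effect of stopping, no standard deviation and no power calculation. The check is a comparison of rules, followed by an illustration on stated assumptions.

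**1. How each background factor is handled before baseline and during treatment**

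| Factor | At entry or baseline | During treatment | Same at both? |
|---|---|---|---|
| Lower urinary tract medicines (inclusion 13) | allowed | dose held stable | yes |
| Diet (Section 4.1) | current habits | current habits kept | yes |
| Systemic hormones (exclusion 11, Section 6.8) | excluded | forbidden | yes |
| Formal pelvic floor therapy (exclusion 1, inclusion 12) | none within 6 months | may not be started | yes |
| Self-directed Kegels (Section 4.1) | not addressed | barred | not assured |

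Only the last row permits a forced change at first dose.

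**2. Shift in the mean change**

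Let p be the share of subjects exercising at baseline and r the proportional rise in their leaks on stopping. If exercisers have the same mean baseline as the others, shift = p × r × baseline mean.

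- Assumed ranges: p = 0.10 to 0.40; r = 0.10 to 0.40.
- Low end: 0.10 × 0.10 = 0.01, or 1% of baseline.
- High end: 0.40 × 0.40 = 0.16, or 16% of baseline.
- At an assumed mean of 6 leaks/day: 0.01 × 6 = 0.06 to 0.16 × 6 = 0.96 leaks/day.
- A middle case: 0.20 × 0.25 × 6 = 0.30 leaks/day.
- Inclusion 8 allows 4 to 15 leaks on each diary day. The low end at 4 is 0.01 × 4 = 0.04, and the high end at 15 is 0.16 × 15 = 2.4 leaks/day.

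The signed rank test works on ranks of the changes, so the mean shift describes the summary statistics better than it describes the test.

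**3. Effect on the test, by simulation (2,000 runs)**

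Assumptions: 30 completers; change of −1.5 leaks/day apart from any exercise effect; SD of change 2.5; two-sided 0.05. The plan states neither alpha nor sidedness.

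| Share exercising | Rise on stopping (leaks/day) | Mean shift | Chance of significance |
|---|---|---|---|
| 0% | none | 0 | 88% |
| 20% | 1 | 0.2 | 75% |
| 20% | 2 | 0.4 | 59% |
| 40% | 1 | 0.4 | 63% |
| 40% | 2 | 0.8 | 27% |

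On a baseline of 6, rises of 1 and 2 leaks/day are 1/6 = 17% and 2/6 = 33%, inside the range in step 2. The results depend entirely on the assumed SD and change.

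**4. Scale against the cited duloxetine trials (Section 2.1)**

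Placebo-arm reductions were 41% and 27%. At 6 leaks/day these are 0.41 × 6 = 2.46 and 0.27 × 6 = 1.62 leaks/day, both favourable. The high-end exercise shift of 16% is smaller than either.

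**The case against.** Several counter-arguments have force.

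- **Exclusion 1 may already cover it.** Section 2.1 moves freely between rehabilitation and exercise programme, so an investigator might count home Kegels as physical therapy. But the protocol uses different terms in exclusion 1 and Section 4.1, and the text leaves home exercisers eligible.
- **She may stop at consent.** The agreement could be applied from Screening. The text does not say so. Even then, the window of Days -21 to 0 gives at most three weeks without exercise before baseline, against at least 12 by Week 12.
- **The cited evidence is about gaining, not losing.** Section 2.1 reports effects of structured training; it reports nothing on stopping, or on unsupervised exercise. This stands, and it is why the size cannot be derived.
- **Non-drug therapies are already recorded.** Section 6.8 requires this, and Table 1 has a concomitant medication row at Screening and at Visits 1 to 6. This stands in part: exercisers might be identifiable, although nothing asks about Kegels by name.
- **Abstinence is a legitimate design.** It is, provided it also holds before baseline.

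A reader might infer that the trial is likely to look falsely negative. The documents do not support that. In an uncontrolled comparison, favourable change of the size seen in the cited placebo arms would exceed the illustrated exercise effect. A reader might also infer bias in the MRI endpoint. The cited imaging findings concern the urethra and its striated sphincter, whereas Section 3.3 names the levator hiatus area and diameters and leaves other parameters open. Finally, with a single site, uneven application between sites cannot arise.

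**Conclusion.** The gap in the rules is real. Section 4.1, the criteria in Sections 5.1 and 5.2 and the visit schedule in Section 7.1 together allow a woman to exercise through her baseline measures and be told to stop when dosing starts. Following the plan exactly could then confound the change from baseline, most likely against the drug.

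The confidence belongs to the gap, not to the bias. The documents do not show that any enrolled woman was exercising at baseline, so the mixing is possible and not established. The 1-16% of baseline rests wholly on assumed shares and rebounds of 10-40% each; the low end is negligible. Women who exercise and still meet the leakage, pad weight and stress test criteria leak substantially despite exercise, so a rebound near 40% would need support that the documents do not give. The point is worth correcting because the correction is cheap and the design has no other protection against it.

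**What to change.** 1. Reconcile Section 4.1 with Sections 5.1, 5.2 and 6.8 and the Protocol Summary so that one exercise rule applies both before the baseline measures and at Week 12. Two routes achieve this: a stability rule running from Screening through follow-up, or abstinence with an entry exclusion that covers self-directed exercise before baseline. The choice is the sponsor's.
2. Under the existing non-drug therapy recording in Section 6.8, ask explicitly about Kegel exercise at Screening and at Week 12.
3. In Section 10.1, add a descriptive report of the primary change with and without women who were exercising at baseline.

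The cost is protocol wording, one CRF item and one extra summary. The exclusion route loses some candidates at screening. The stability route keeps them but adds some exercise variability, and leaves open that drug and exercise act together in those women; the with-and-without summary would help show how far they drive the result.

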4.2 MEDICAL MONITORING

A Medical Monitor will be responsible for monitoring the safety and data of this trial. The data that will be monitored include adverse events related to the study drug and procedures.

5. STUDY ENROLLMENT AND WITHDRAWAL

5.1 SUBJECT INCLUSION CRITERIA

Subject Inclusion Criteria: Subjects eligible for inclusion in this study must meet **all** of the following criteria:

1. Give voluntary, written and signed, informed consent
2. Female
3. Age 18 to 80 years old
4. Clinically confirmed as postmenopausal. Subjects must have undergone the onset of spontaneous, medically induced or surgical menopause prior to the start of this study. Postmenopausal is defined as 12 months of spontaneous amenorrhea or 6 months of spontaneous amenorrhea with serum FSH levels > 40 mIU/ml or 6 weeks postsurgical bilateral oophorectomy with or without hysterectomy.
5. SUI symptoms for at least 6 months duration
6. Predominant SUI (MESA questionnaire)
7. 24 hour pad weight >3 gms at baseline
8. At least 4, but no more than 15, SUI episodes on each day of the 3 day baseline voiding diary.
9. Serum AST and ALT within normal limits
10. Total bilirubin within normal limits
11. Positive Bladder Stress Test
12. Subject agrees to not start any new treatment (medication or otherwise) that is known to affect lower urinary tract function throughout the treatment and follow up periods.
13. Subject agrees to maintain on a stable dose of any medication known to affect lower urinary tract function, including but not limited to anticholinergics, tricyclic antidepressants, or alpha-adrenergic blockers, throughout the treatment and follow-up period.

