2. INTRODUCTION: BACKGROUND INFORMATION AND SCIENTIFIC RATIONALE

2.1 BACKGROUND/RATIONALE

Stress urinary incontinence (SUI), the involuntary leakage of urine during activities that increase abdominal pressure (e.g. coughing, sneezing, physical exercise), affects up to 35% of adult women (Luber, 2004). Urinary incontinence and pelvic floor disorders are major health problems for women especially as they age.

There are a variety of treatments that may be used to treat SUI in women (Rovner, 2004). Behavioral modification and pelvic floor physical therapy are common initial treatment approaches even though surgical procedures (e.g. sling; bladder neck suspension) are often ultimately the most effective. Biological and other materials for injection into the urethra have also been marketed for treating intrinsic sphincter deficiency (ISD), a cause of SUI symptoms. In a study of autologous fat injected into the urethral sphincter only 22% of patients improved compared to 21% after placebo injection (Lee, 2001). However, the injection of muscle derived stem cells (AMDC) is a promising new therapy for SUI currently being tested in clinical trials. In a dose escalation study of AMDC, injected into the urethral sphincter, all dose groups had significantly fewer diary stress leaks at 12 months, but only patients who received the highest dose of AMDC had statistically significant reduction in mean pad weight (Peters, 2014). Pharmacologic therapies for SUI also have been tested with varying results. In a study of duloxetine (a selective serotonin reuptake inhibitor), the median incontinence episode frequency decreased 41% in the placebo group compared to 54% receiving duloxetine 20 mg/day, 59% for duloxetine 40 mg/day, and 64% for duloxetine 80 mg/day (Norton, 2002). Dmochowski and colleagues also demonstrated a statistically significant reduction in incontinence episode frequency with duloxetine therapy compared with placebo (50% vs 27%, respectively) (Dmochowski, 2003).

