6.8 CONCOMITANT MEDICATIONS/TREATMENTS

Forbidden medications and treatments during the study duration include:

- Systemic hormonal products including but not limited to estrogens, progestins, testosterone, methyltestosterone, oxandrolone (Oxandrin[®]), oxymetholone, danazol, fluoxymesterone (Halotestin[®]), other androgenic compounds, including herbals. Intravaginal application of estradiol topical/tablet agents and hormones delivered via vaginal ring are allowed.
- Treatment with any investigational agent within 6 months before the first dose of study treatment;

Previous and Concomitant Medication (Drugs and Therapies)

The Investigator or designee must record the use of previous (all medication taken within 30 days prior to Screening (Visit 1) and current concomitant treatment, both drug and non-drug therapies, prescribed and over-the-counter and all alternative medicines, in the CRFs. This also includes drugs used on a chronic and as-needed basis. Subjects must be instructed not to start any new medication, both prescribed and over-the-counter, without consulting the Investigator, unless the new medication is required for emergency use. Subjects must be instructed to notify the Investigator immediately if medications were required for emergency use.

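### The rules against changing other continence treatments begin only with the treatment period, so a medication or Kegel-exercise change shortly before or during screening can enter the uncontrolled change from baseline, in either direction

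*Combined protocol and SAP*

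**What the plan says.** Section 5.1, inclusion 12, reads in part "Subject agrees to not start any new treatment (medication or otherwise) that is known to affect lower urinary tract function throughout the treatment and follow"; the words left out only complete its reference to the follow-up phase. Inclusion 13 asks for a stable dose of medication that affects lower urinary tract function, "including but not limited to anticholinergics, tricyclic antidepressants, or alpha-adrenergic blockers, throughout the treatment and follow-up period". The synopsis (Section 1) repeats both. Section 4.1 repeats them again and adds "Subjects will also agree to refrain from performing any Kegal exercises and maintain current dietary habits throughout the treatment and follow up periods".

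Some other treatments do have a look-back. Section 5.2 excludes "Pelvic floor physical therapy within the last 6 months", and it excludes any earlier SUI procedure or surgery without time limit. Section 6.8 bars "Treatment with any investigational agent within 6 months before the first dose of study treatment", but that rule stands in a list headed as prohibitions during the study and is absent from the exclusion lists in Section 5.2 and the synopsis.

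Exclusion 11 covers "Subjects taking systemic hormone products", gives no interval since stopping, and exempts vaginal estradiol and vaginal rings. Section 6.8 has sites record "all medication taken within 30 days prior to Screening" and tells subjects to consult the investigator before starting a medication.

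Under Section 7.1 and Table 1, the diary is explained at Screening, completed before Visit 1 and collected at Visit 1, where the first dose is taken. Eligibility is checked at Screening and again at Visit 1.

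**The concern.** The study has one arm, and the primary result is each woman's change from her own baseline diary (Sections 3.3 and 10.1). That comparison is clean only if other influences on leakage are steady from the baseline diary to Week 12. The criteria protect the interval after the first dose but not the weeks before it. A treatment begun or dropped in those weeks may still be taking effect, or wearing off, after the diary has been recorded. The trial would then report that movement as part of the change on GTx-024. Section 10 plans no covariate, exclusion or sensitivity analysis for recent treatment changes.

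**Working it through.** **Plan figures.** The plan gives no figure for this bias. The only plan number needed for the denominator is 30 completers (Section 10). Recruiting up to 35 to obtain 30 implies withdrawal of 1 - 30/35 = 14.3%, inside the stated 10-20%; the point does not depend on it.

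**Step 1: what is required before baseline.**

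- Pelvic floor physical therapy: none within 6 months (5.2).
- SUI procedure or surgery: never (5.2).
- Investigational agent: none within 6 months of first dose (6.8 only).
- Systemic hormones: not currently taken; no interval since stopping (5.2).
- Vaginal estradiol and rings: allowed; no period of stable use required.
- Other medication affecting lower urinary tract function: nothing before the treatment period.
- Kegel exercises: barred only during treatment and follow-up (4.1).

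The last three leave the weeks before baseline open, and the fourth covers only current use.

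**Step 2: what reaches the endpoint.** If another treatment contributes e(t) to daily episodes at time t, its contribution to the change is e(Week 12) - e(baseline diary).

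- Effect settled before the diary: e is equal at both times, and the contribution is zero.
- Change shortly before the diary: only the part that develops afterwards counts.
- Change between the diary and Visit 1: the whole effect counts.

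Starting a helpful treatment exaggerates the fall; stopping one masks it. A woman who does Kegel exercises during her baseline diary must stop once treated, so Section 4.1 itself can alter her condition between the two diaries.

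**Step 3: ceiling from the protocol's own duloxetine figures.** Section 2.1 reports that "the median incontinence episode frequency decreased 41% in the placebo group compared to 54% receiving duloxetine 20 mg/day", with 64% at the highest dose.

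- Excess over placebo: 54 - 41 = 13 to 64 - 41 = 23 percentage points.
- Inclusion 8 allows 4 to 15 episodes/day. Per affected woman: 0.13 x 4 = 0.52 to 0.23 x 15 = 3.45 episodes/day.
- Assume 3 of 30 are affected: 0.52 x 3/30 = 0.05 to 3.45 x 3/30 = 0.35 episodes/day on the mean.

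This treats a median percentage change as an individual change and assumes that the full effect develops after the diary.

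**Step 4: a second range, by assumption.** Let each affected woman have an extra fall of 1 to 3 episodes/day. Mean bias = (number affected / 30) x shift. The last column is the simulated rejection rate of a two-sided 5% signed-rank test (normal approximation), with 30 women, an assumed SD of change of 1.5 to 2.5, and neither drug effect nor placebo response.

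| Affected of 30 | Mean bias, episodes/day | Rejection rate |
|---|---|---|
| 1 | 0.03-0.10 | about 5% |
| 3 | 0.10-0.30 | 5-10% |
| 6 | 0.20-0.60 | 6-28% |
| 9 | 0.30-0.90 | 9-60% |

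With 3 affected, the bias runs from 0.10/9.5 = 1.1% of baseline, at the midpoint of the entry range, to 0.30/4 = 7.5% at its lower limit.

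**The case against.** The strongest reply is that the bias is minor beside what the design already accepts. The placebo fall of 41% in the same source, over 4 to 15 episodes/day, is 0.41 x 4 = 1.6 to 0.41 x 15 = 6.2 episodes/day. Against that, the Step 3 ceiling is 0.05/1.6 = 3% to 0.35/6.2 = 6%. The stated objective is to describe, in a feasibility study without a power calculation. This stands, and it limits how much weight the point can carry.

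A second reply is that existing text closes the gap. A stable dose can be read as presupposing stability at entry, but no duration is given. The consult-first instruction in Section 6.8 has no start date, does not address stopping a drug and carries no eligibility consequence. The investigator-judgement exclusion concerns risk to the subject, not confounding. The 30-day record would let most recent medication changes be identified, but nothing in the plan uses it.

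Three stronger readings are tempting, and the documents do not support them.

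- A reader might infer that every rule on continence treatments starts with dosing. Physical therapy, SUI procedures and investigational agents all have look-backs.
- A reader might infer that a woman could stop systemic hormones the day before Visit 1 and qualify. Eligibility is also checked at Screening, and the three-day diary separates the two visits, so she would meet exclusion 11 at Screening. Only stopping before Screening escapes it.
- A reader might infer that the other treatment's whole effect is credited to GTx-024. Only the part still evolving after the diary counts, and it can work against GTx-024.

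**Conclusion.** The gap is real. Followed exactly, the plan admits women whose medication or Kegel exercise changed shortly before or during screening, and any effect still evolving after the diary goes into the primary change. The direction is not fixed. The size is modest: at most about 0.05 to 0.35 episodes/day on the mean if 3 of 30 are affected, and appreciable only if several women are. The number affected is assumed, and the per-woman effect is borrowed from the duloxetine figures; the documents give neither for this population. The case for acting is that the remedy is cheap and that no other comparison in the trial would reveal the problem. The placement of the investigational-agent rule is a separate inconsistency: a woman can pass the eligibility list and still breach Section 6.8 at her first dose.

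**What to change.** 1. In Sections 1, 4.1 and 5.1, add an entry condition, worded as a fact at entry and not as a promise: treatments affecting lower urinary tract function, naming vaginal estradiol, vaginal rings and Kegel exercises, have been unchanged for a sponsor-defined period before Screening and through the baseline diary. The existing rules then continue through Week 16. The 30 days already recorded under Section 6.8 is a convenient window. Section 6.8 labels Screening as Visit 1, whereas Table 1 makes Visit 1 the Baseline visit, so the anchor needs to be made consistent.
2. Have the sponsor state how recently stopped systemic hormones are handled under exclusion 11. Any interval is the sponsor's clinical decision.
3. Reconcile Section 6.8 with the eligibility lists by placing the existing 6-month investigational-agent rule in Section 5.2 and the synopsis.
4. Add to Section 10.1 a sensitivity analysis of the primary endpoint that omits women with a recorded change in the 30 days before Screening or during screening.

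Cost: protocol wording and one extra analysis. The medication history is already collected; Kegel exercises should be asked about explicitly, because the record of non-drug therapies does not name them. A few candidates will be delayed or will fail screening.
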